In the second part of the study we will enroll from 60 to 70 serodiscordant couples. All HIV serodiscordant couples entering the second part of the study will be administered a baseline, 6-, 12-, and 18-month survey. We will collect ongoing clinical data from each clinic visit, and from the larger clinic population for comparison. Positive partners engaged in care as a dyad will have a viral load test at 18-months. Biometric data (fingerprint) will be collected at study and intervention encounters to link utilization of services with survey data. We will also enroll serodiscordant couples from patients already receiving care from the Kisarawe Care and Treatment Center (CTC). To ensure serodiscordant couples who participated in the self-testing phase have an opportunity to enroll in the second part of the study, we will keep enrollment open until approximately 1-month after the target enrollment for the second part of the study is reached. Based on historical rates of serodiscordant status among couples we estimate that we will need to enroll approximately 442 couples to identify 60 couples for the second part of the study, however, it may take up 1000 couples in the first part of the study to find this many serodiscordant couples. Additionally, since we will be conducting the HIV self-testing by geographic cluster, we will offer HIV self-testing to all eligible persons in each cluster that we start to avoid denying people in the geographic clusters access to HIV self-testing and also biasing our sample. This may result in us completing the enrollment of the 60 couples for the second stage of the project while still providing HIV self-testing in the first stage of the study. Thus, we may need to exceed the N of 60 as we complete the final geographic cluster with HIV self-testing to assure that those found to be discordant through self-testing have an opportunity to engage in the second part of the study. We thus may have up to 70 couples enrolled in the second part of the study. Because of the diversity in recruitment strategies, we will be able to track uptake of care between those newly diagnosed with HIV and those with previous diagnoses who have already begun receiving care.

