This is an ideal study setting. The intervention strategy we propose is based on our extensive experience conducting large-scale HIV prevention trials in Tanzania for over 17 years in collaboration with Muhimbili University. Over the past 8 years we have collected extensive data on HIV risk and

household characteristics from NIMH Project Accept – a multi-site community randomized Phase III trial assessing the efficacy of community-based HIV voluntary counseling and testing. We have mapped and enumerated all households in the district, done qualitative research, characterized HIV risk factors (behavioral and biologic), done cost-analyses, worked successfully with the local communities and health system, established a collaboration with the PEPFAR-funded AIDS treatment centers, and established a rural research infrastructure with experienced intervention and research staff. Our specific AIMS evaluate 4 key strategic goals, including:

1. HIV Self-Testing for Stable Couples: (a) assess the acceptability, safety, and factors associated with uptake of HIV self-testing; and (b) determine the proportion of clients testing positive for HIV via self-testing who engage in care.
2. Dyadic Engagement of Serodiscordant Couples in Care & Prevention: (a) establish the proportion of serodiscordant couples who will enroll in HIV care as a dyad, (b) determine the effect of dyadic care enrollment on retention and adherence, and (c) assess reduction in risk of acquiring HIV infection for the negative partner.
3. Pre-Exposure Prophylaxis (PrEP): (a) establish the proportion and characteristics of HIV negative clients in a serodiscordant relationship who opt to take PrEP, (b) determine how engaging in ARV treatment by the positive partner affects PrEP utilization by the negative partner, and vice versa, and (c) Identify patterns and correlates of risk reduction strategies that couples in care utilize over time (abstinence, ARV for positive partner, PrEP for negative partner, condom use).
4. Operational: (a) determine Dyadic-based Diagnosis, Care, & Prevention (DDCP) program cost and economic efficiency, (b) compare DDCP to clinic-based and mobile VCT with regard to cost and efficiency for testing and linkage to care, and (c) assess the feasibility, acceptability, safety, and utility of using biometric data to track service utilization.

B. BACKGROUND AND SIGNIFICANCE

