Enumeration of Household Members – When a household is approached for potential participation in the study, data collectors will explain the study, and with verbal consent of the head of household, establish if there are eligible couples within the household. Recruitment and Data Collection - Couples selected for inclusion will be invited to participate in the study. Couples are defined as two persons in an ongoing sexual relationship of at least 6-months, and each of these persons considers the other to be a “partner” in the relationship. To be eligible for participation, each individual has to be 18 years or older, live in the household regularly (thus, we are focused on cohabitating couples), and with no plans for moving from the area before the follow up period. Both members of the couple need to be aged 18 years or above, and at least one member of the couple must be aged 55 years or below. Additionally, each member of the couple must be willing to disclose their HIV status to their partner following self-testing, either facilitated by a counselor by the couples themselves. Before beginning the consent process, the interviewer will verify eligibility with the individual with respect to residency and age information. If the selected individual is not available during the household visit, the interviewer will be required to return to the household a minimum of two times (on different days/times of day) to locate the selected individual, request consent, and conduct the interview. Each member of eligible couples will be consented separately and in private, and consent of both members is required for entry into the study. Privacy will be ensured by having the consent and interview take place in a location where conversations cannot be overheard and the participant feels comfortable. If a couple declines to participate, they will be asked if they would be willing to tell us why. They will be consented for this process. At two weeks after leaving the self-testing kits with couples, data collectors shall return to study cohort members and repeat data collection (survey & blood for follow up interview). At this time, data collectors will collect any unused test kits and will also collect used test kits (sealable envelopes will be provided to participants to keep test kits after use). All collected test kits will be taken to the Study Center and kept in designated biohazard bins before being incinerated at the collaborating government health facility adjacent to the Study Center. At six months, a subset of participants will be approached to complete a follow up survey. The subset will consist of 50% of participants who were confirmed HIV positive (but no less than 20) and 5% of participants who tested negative (but no less than 10). For recruitment at the CTC, we will raise awareness about the study with existing CTC patients. If interested, these patients will be provided a card they can give to their partners to come and receive HIV testing through the study. The patients themselves will not have to retest for HIV since they are already receiving HIV-related care. The negative partner will receive HIV confirmatory testing at the Study Center. Serodiscordant couples in the area found through this recruitment strategy will be offered participation in the study. Similar eligibility criteria and definition of a “couple” used for the self-testing recruitment will also be used for the CTC-based recruitment (with the addition of residing near or within Kisarawe Ward). For CTC-based recruitment, written informed consent from both partners, completed individually and in private, will be required for entry into the study.

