
Confirmatory HIV Voluntary Counseling and Testing Two weeks after the self-testing has been offered, we will return and offer confirmatory testing. Standard blood-based rapid tests will be offered to all participants who present with report of a positive HIV self-test result. A fingerprint scan will be taken, and a survey will be conducted. We will offer to provide HIV testing to both partners and will only do this jointly with the couple (sharing the results) with each member's consent. Individual HIV confirmatory testing will also be offered if preferred. We will utilize Tanzanian and WHO/CDC standards for provision of VCT, and have vast experience conducting VCT in the area, and in training and monitoring staff conducting VCT. If clients have trouble using the self-test kits, couples can come to the Study Center where they can receive standard HIV testing and counseling services with trained counselors.

[figure not shown]
Referral Counseling will be offered for any client with a confirmed positive HIV test result. Concordant seronegative couples will be advised to retest in 6-months, following national guidelines. Concordant seropositive couples will be counseled on the importance of HIV treatment and will be offered an escort to the CTC for services. Serodiscordant couples will be reminded of the option for them to enter care and treatment as a couple as part of the study intervention, and that the negative partner will have the opportunity to receive PrEP through the study. In addition, the counselor will review with the couple the clinical risks and benefits of PrEP and seek consent for them to be interviewed again in 6-months and 12-months (in addition to the 18-month scheduled interview). If the positive partner is not already enrolled in care, they will be offered an escort to the CTC to schedule an appointment.

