Enrollment in HIV Care as a Couple. Consent will be confirmed to enter care as a study participant. The staff member will explain that the positive partner is eligible for HIV-related treatment regardless of their CD4 count and will remind the couple that the positive partner is eligible for care, according to the national guidelines, should they not want to enter the study. A Study Nurse will review again the benefits and risks associated with PrEP, and the preventative benefits of ARV use with regard to reduction in HIV transmission to the negative partner. In addition, a month's supply of condoms will be provided to the couple, and staff will inform them that they can return for more condoms as needed, and they will be counseled on the preventative benefits of condom use and sexual abstinence. The positive partner will then be referred to the CTC Medical Officer who will conduct a medical assessment and following national guidelines, establish a treatment regimen for the positive partner. In many cases, families share a cellphone. In order to be able to communicate with participants and add a layer of protection to confidentiality, we will provide an inexpensive cell phone to each participant. In

addition, both partners will be asked their preferred alternative communication methods in the event we are unable to reach them using the provided study phones or they are unable to make it to the study office for the 6-, 12-, and 18-month study visits.

The Negative Partner will be Offered PrEP.

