AIM 3 - We hypothesize that a moderate proportion of HIV negative partners will utilize PrEP (~ 30%), that PrEP utilization among HIV negative partners will be associated with lack of ARV use by positive partners, and ARV use by positive partners will be associated with lack of PrEP use by negative partners. To evaluate the factors associated with uptake of PrEP, a single level logistic regression model with a logit link function will be performed. Demographic variables such as age and gender will be evaluated as predictors of PrEP uptake, with the results focusing on the odds ratios, and corresponding 95% confidence intervals, for these variables. To evaluate association between ARV and PrEP utilization within couples, two main models will be performed. For the first, the outcomes will be variables related to the use of PrEP. Likewise, for the second, the outcomes will be variables related to the use of ARV. These outcomes will be evaluated using MRMs as described above. Because each outcome is specific to one member of the couple (i.e., the negative partner for PrEP and the positive partner for ARV), the data will have a two level structure with repeated measurements (level-1) nested within couples (level-2). At the repeated measurements level of the model, the partner's ARV or PrEP status for the preceding time period will be entered as a time-varying covariate. For example, for the PrEP outcome, the positive partner's ARV status will be entered at level-1, and this will test for differences in the use of PrEP for negative partners whose positive partners were on ARV versus not on ARV. Similarly, for the ARV outcome, the negative partner's PrEP status will be entered at level-1, and this will test for differences in the use of ARV for positive partners whose negative partners were on PrEP versus not on PrEP. More tailored formulations are also possible. For example, introducing a lag between the predictor and outcome could test the extent to which PrEP and ARV status were associated with later initiation of ARV or PrEP. **We hypothesize couples will alternate risk reduction strategies (abstinence, ARV treatment for the positive partner, PrEP for the negative partner, and condom use) but typically maintain at least one strategy.** Each risk reduction strategy will be considered as a separate outcome, with repeated measurements of strategies (level-1) nested within couples (level-2). The model specification will be heavily informed by preliminary evaluation of the spaghetti plots, as described above. These plots will guide tests for patterns of change over time (e.g., linear), specific phases of change, or even invariance over time such that aggregation is justified. After building the mixed-effects model, predictor variables related to the use of abstinence, condoms, ARV, or PrEP will be added to the model. These variables will also be considered for entry as time-varying covariates (i.e., entry at level-1) or as aggregative, couple-specific predictors based on the findings of the previous models. Such a formulation will test for, for example, differences in the use of risk reduction strategies for time periods when the positive partner is on ART versus not on ART. Based on the descriptive statistics and the patterns of use of each individual strategy over time, supplemental analyses will be considered that simultaneously evaluate all of the strategies. For instance, cluster analyses could be used to identify groupings of individuals based on the combination of risk reduction strategies utilized.

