Pregnant or breast-feeding HIV-negative women who join the HIV serodiscordant couple component of the study will be allowed to take PrEP as Truvada has shown no increase in adverse effects related to fetal/infant health, both when used as PrEP⁹⁰ and when used as treatment for HIV. It will be a woman's choice whether to continue using PrEP during pregnancy and breast-feeding after discussing the risks and benefits with the clinical officer. Age does not impact potential risks to participants. However, at least one member of the couple should be aged 55 years or below to be eligible for participation. Other potentially vulnerable populations will not be included in the proposed clinical trial.

To help prevent lost to follow-up occurrences, serodiscordant couples recruited from the CTC must reside within or near Kisarawe Ward. Potential participants who do not reside within or near Kisarawe Ward will be excluded. The following towns are considered near Kisarawe Ward for the purposes of this study: Chanika, Masaki, Pugu, Minaku, Msimbu/Homboza, Kazimumbwi.

Due to the need to collect ongoing clinical data at the Kisarawe CTC, positive partners who choose to enroll into care at a CTC other than the Kisarawe CTC, will not be allowed to participate in the second phase of the study.

Age does not impact potential risks to participants. Other potentially vulnerable populations will not be included in the proposed clinical trial.

Individuals under the influence of drugs or alcohol and anyone presenting with mental disability that would preclude ability to understand study procedure, risks, and benefits will be excluded from participation.

All human subject data will be collected within the study communities by staff at Muhimbili University of Health and Allied Sciences (IRB FWA00004301), subcontractor to The Medical University of South Carolina (MUSC). Source documents will be stored securely at Muhimbili facilities and managed by Muhimbili and MUSC research personnel. Data will be collected using IRB approved data collection instruments.

Inclusion of Women and Minorities

1. All households within a certain geographic area will be approached to participate in the study. The distribution of men in women in the study communities is thought to be relatively equal, and the vast majority of men and women live jointly in mixed gender households. It is thus expected that the makeup of those invited to participate in the study will have no gender bias.

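### Entry into care is fixed in advance for the previously diagnosed group, and the Aim 2 couple-versus-clinic models name no term separating new from established patients

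*Combined protocol and SAP*

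**What the plan says.** The opening overview describes two routes into the serodiscordant cohort: household self-testing, and existing patients of the Kisarawe CTC. It then says that this diversity will allow the study to "track uptake of care between those newly diagnosed with HIV and those with previous diagnoses who have already begun receiving care".

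The recruitment section says of the CTC route: "The patients themselves will not have to retest for HIV since they are already receiving HIV-related care". For couples who come through self-testing, the referral counseling text says: "If the positive partner is not already enrolled in care, they will be offered an escort to the CTC to schedule an appointment".

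Sampling of Households says that both routes run until 60 couples (up to 70) are enrolled. It sets no target or cap for either route.

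The formal aim on entry into care is Aim 1(b), to "determine the proportion of clients testing positive for HIV via self-testing who engage in care". This is a single-group proportion.

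The Aim 2 analysis compares positive partners enrolled as a couple with patients in routine clinic services, on retention, 18 monthly refills and 18-month CD4, using a person-level indicator for couple versus routine. For Aim 3 the plan says: "Demographic variables such as age and gender will be evaluated as predictors of PrEP uptake". Neither aim names diagnosis timing, recruitment route or time in care as a model term.

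**The concern.** There are two linked problems.

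First, the overview offers a comparison in which one group is defined by having already reached the outcome. A report that set all newly diagnosed people beside the CTC recruits would show a shortfall that comes from the definition and says nothing about the intervention.

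Second, the same mixture enters the Aim 2 comparison. The Background cites a systematic review that found patients lost at each stage between testing and starting ART. Established CTC patients have already passed those stages, while newly diagnosed patients have not. If Part 2 and the routine clinic group hold different shares of new patients, a difference in retention or refill partly reflects those shares. The plan names nothing that would separate this from an effect of dyadic care.

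**Working it through.** The documents give no sample size, precision or power for a new-versus-previous contrast, so there is no figure of the plan's to reproduce. The check is partly logic and partly arithmetic under stated assumptions.

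**1. Entry into care as the outcome.** Let U be the proportion of newly diagnosed people who enter care. The previously diagnosed group is at 100% by selection, so the difference is U − 100%.

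| U (assumed) | Difference |
|---|---|
| 50% | −50 points |
| 70% | −30 points |
| 90% | −10 points |
| 100% | 0 |

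The difference is a relabelling of U, and U is what Aim 1(b) estimates.

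**2. Outcomes that are not fixed.**
- *Dyadic enrolment.* The qualitative sub-study section reports about 40 serodiscordant couples who knew of the study and did not join, and plans interviews with non-participants from both routes. Against 60 to 70 enrolled, crude uptake is 60/(60+40) = 60% to 70/(70+40) = 64%. The 40 is a snapshot, so this is only an order of size.
- *ARV uptake.* Formative Research describes CTC patients in care but not on ART. Part 2 makes the positive partner eligible for treatment whatever the CD4 count.
- *PrEP uptake, refill and retention.* All are measured after entry, and recruitment route fixes none of them.

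**3. Effect of the mix on Aim 2.** Let w and v be the shares of newly diagnosed patients in Part 2 and in the routine group, and let R_new and R_est be the retention proportions. If dyadic care has no effect, the crude difference is

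(w − v) × (R_new − R_est).

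The documents give none of these four quantities. For illustration, assume that the routine group is all established (v = 0). Assume also that the Part 2 split lies between 20:80 and 50:50 with either group the smaller, so w is 0.2 to 0.8. Each 10-point gap between new and established patients then moves the crude comparison by 0.2 × 10 = 2 to 0.8 × 10 = 8 points. The direction depends on the sign of both brackets and cannot be settled from the documents.

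**4. Precision of a new-versus-established difference in Part 2.** The 95% half-width is 1.96 × √[p(1−p)/n₁ + p(1−p)/n₂]. Take p = 0.70, so p(1−p) = 0.21. The 70% is Aim 2's hypothesised dyadic engagement and serves here only as a plausible level.

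| Couples | 50:50 split | 20:80 split |
|---|---|---|
| 60 | 30/30: ±23 points | 12/48: ±29 points |
| 70 | 35/35: ±21 points | 14/56: ±27 points |
| 50 completers | 25/25: ±25 points | 10/40: ±32 points |

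Worked case: 1.96 × √(0.21/30 + 0.21/30) = 1.96 × 0.118 = 0.23.

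At 60 couples, 80% power (two-sided 0.05 assumed) against 70% in one group needs about 97–98%, or 27–35%, in the other. The contrast can be estimated, but only descriptively.

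**The case against.** The strongest reply is that the sentence speaks of tracking and no test is planned. None of the four aims, their hypotheses or the precision section contains a new-versus-previous contrast, and the protocol calls the study exploratory. Uptake can also be read as uptake of dyadic care, ARV or PrEP, none of which is fixed for CTC recruits. All of this stands, and it limits the first problem to one of wording.

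The model specifications are also not closed. The Aim 3 list of demographic predictors is illustrative, and the fourth Aim 2 outcome allows predictors related to risk. A diagnosis-timing term could be added under that wording. But it is not named, and the couple-versus-routine models for retention and refill mention only the couple indicator.

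A reader might go further and infer that joining Part 2 requires being in care, so that any comparison inside Part 2 is empty. Two sentences invite this: "Consent will be confirmed to enter care as a study participant", and the rule that "positive partners who choose to enroll into care at a CTC other than the Kisarawe CTC, will not be allowed to participate". The second excludes care at a different center; it does not exclude being in no care. The escort for those not yet enrolled is an offer. No listed criterion makes care a condition of entry. If one did, both groups would be at 100% and the difference would be zero, not a built-in gap.

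It is also tempting to test 70% against 100% at Part 2 group sizes and report the gap as significant. The 70% is a couple-level expectation among those presenting at the referral office. It is not individual linkage among newly diagnosed people, and the documents plan no such test.

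**Conclusion.** The point holds in limited form. Read as entry into care, the comparison offered in the overview carries no information beyond Aim 1(b), but no planned conclusion rests on it. The documents do not support the broader inference that new and previously diagnosed people cannot usefully be compared at all.

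The consequence worth acting on is in Aim 2. Part 2 mixes two kinds of patient in a ratio that is not controlled, and the couple-versus-routine models name no term for it. The size of any bias is unknown. Under the illustrative assumptions above it is 2 to 8 points for each 10-point gap in retention between new and established patients. This depends on the assumed shares and on a retention gap that the documents do not quantify.

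Recruitment route is only a proxy for diagnosis timing, because the referral text allows for self-testers who are already in care.

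**What to change.** 1. Reword the overview sentence so that entry into care is reported only as the Aim 1(b) proportion among confirmed self-test positives. Show separately those already enrolled at a CTC before self-testing, since otherwise the same selection returns.
2. Classify each positive partner as new or established from the CTC2 enrolment record relative to study entry, with recruitment route as back-up. The documents say that CTC2 records enrolment; confirm that the field holds a usable date.
3. Report dyadic enrolment, PrEP uptake, refill, retention and 18-month viral suppression in Part 2 separately by this factor, as descriptive results with confidence intervals. For dyadic enrolment, give each route its own denominator.
4. Add the factor, or time since CTC enrolment derived in the same way for study and routine patients, as a covariate in the Aim 2 couple-versus-clinic models.

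The cost is a wording change, one derived variable from data already planned, and one parameter in models with 60 to 70 study couples. Stratum intervals will be wide. If nearly all routine patients are established, the covariate's effect will be estimated mainly within Part 2. Residual confounding by time since diagnosis will remain and should be stated.
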